#### **4.4 Design Justification**

This study represents one of the first repurposed investigations of Ifenprodil in patients with COVID-19 disease. This study will provide information on the safety and clinical efficacy in the SARS-CoV-2 infected population prior to advancing to larger clinical trials, as well as provide critical information for the design of future studies in this population.

The purpose of this study is to determine whether Ifenprodil is effective and safe in the treatment of patients with COVID-19 disease. The primary measure of efficacy will be patient clinical status (on a 7-point ordinal scale) at day 15 in IP versus control group patients. This protocol is based on the recommendations of the [WHO R&D Blueprint Clinical Trials Expert Group](#).

The Phase 2b stage will be an open label study with patients, investigator, site and CRO staff aware of treatment received. The Phase 3 stage of the protocol will also include a placebo arm to allow for double-blinding.

#### 4.5 Dose Justification

20 mg TID:

20 mg TID of Ifenprodil is within the recommended dosing guidelines for other indications as per the manufacturer's package insert.

Assuming a 60 kg person, a single 20 mg dose would yield a 0.333 mg/kg weight adjusted dose. To convert to a mouse dose, a factor of 12 is applied to the human equivalent dose ([Nair and Jacob, 2016](#)), which results in approximately 4 mg/kg for mice.

A 4 mg/kg dose given three times daily (12 mg/kg total daily dose) was found to be efficacious in reducing pulmonary fibrosis, and better than a single 30 mg/kg daily dose in reducing fibrosis in mice. The independent study involving H5N1 infection in mice also used a single daily dose of 20 mg/kg.

Similarly, the single 1.5 mg/kg dose selected in the acute cough model in the guinea pig was also equivalent to the single 20 mg/kg human dose on a body surface area adjusted basis based on an adjustment factor of 4.6.

Thus, the current 20 mg TID human dose is proposed to be a reasonable dose for this initial exploratory study. Please refer to the Investigator's Brochure for additional details on the aforementioned pre-clinical studies.

40 mg TID:

40 mg TID of Ifenprodil is also expected to be a reasonable dose for this exploratory study. Long term pre-clinical toxicological studies suggest dosing up to 16 mg/kg/day should produce no adverse effects. Specifically, the no-observed-adverse-effect level (NOAEL) observed were 50 mg/kg/day (HED of 8 mg/kg/day) in repeat oral dose studies in the rat of up to 52 weeks (Kawai et al, 1975a; Kawai et al, 197b), 30 mg/kg day (HED of 17 mg/kg/day) in dogs of up to 6 months (Nagata et al, 1997), and 50 mg/kg/day (HED 16 mg/kg/day) in rabbit of 30 days (Kawai et al, 1976).

Furthermore, high doses of Ifenprodil (60-300 mg/day) have been used for analgesic purposes in humans. In addition, a trial using 120 mg/day of Ifenprodil for methamphetamine dependence is underway in Japan (UMIM clinical trial registry UMIN000030849; [Kotajima-Murakami et al, 2019](#)) for 84 days. Assuming a 60 kg subject, the proposed 40 mg TID dose in this study is 2 mg/kg/day dose level and limited to 14 days exposure, well within previously used dosing regimens.

#### 4.6 Trial Schedule and End-of-Trial

First patient first visit is planned for the Third Quarter of 2020 and last patient last visit is planned for the First Quarter 2022. The expected total duration of the trial is approximately 18 months.

The End of Trial is defined as the date of the last visit of the last patient to complete the study.

At the end of the trial patients will be treated for their COVID-19 disease at the discretion of the Investigator.

#### 4.7 Trial Stopping Rules and Safety

The Medical Monitor will review AE / SAE data every 2 weeks. If there are a concerning number of unexpected AEs, the DSMB will be asked to review safety data in an ad hoc meeting.

The DSMB will review safety data after every 25 subjects are entered into the trial up to 100 subjects, and then at every 50 subjects; ad hoc reviews will be undertaken if there are other specific safety concerns. The study will not stop enrolment awaiting these DSMB reviews, though the DSMB may recommend temporary or permanent cessation of enrolment based on their safety reviews. Following the recommendations of the of the [WHO R&D Blueprint Clinical Trials Expert Group](#) and given the severity of illness in COVID-19, there are no pre-specified study stopping rules for safety.

## 5. SELECTION OF STUDY POPULATION AND WITHDRAWAL CRITERIA

Deviations from inclusion and exclusion criteria are not allowed because they can potentially jeopardize the scientific integrity of the study, regulatory acceptability or patient safety. Therefore, adherence to the criteria as specified in the protocol is essential.

### 5.1 Inclusion Criteria

1. Male and female subjects aged  $\geq 18$  years of age
2. Confirmed coronavirus infection
  - a) Positive real-time fluorescence polymerase chain reaction of the patient's respiratory or blood specimens for SARS-CoV-2 nucleic acid
  - b) Viral gene sequences in respiratory or blood specimens that are highly homologous to SARS-CoV-2
  - c) Any other diagnostic test accepted by local regulatory authorities
3. Must be hospitalized and requiring supplemental oxygen, or on non-invasive ventilation or high flow oxygen devices (Score of 4 or 5 on WHO Ordinal Clinical Scale)
4. Female subjects of childbearing potential who are sexually active with a non-sterilized male partner must use at least 1 highly effective method of contraception (e.g. oral contraceptives, intrauterine device, diaphragm plus spermicide) from the time of screening and must agree to continue using such precautions for 90 days after the final dose of study drug(s)

5. Non-sterilized males who are sexually active with a female partner of childbearing potential must use condom plus spermicide from day 1 through 90 days after receipt of the last dose of study drug(s)
6. Subjects (or legal designate) must have the capacity to understand, sign and date a written, informed consent form and any required authorization prior to initiation of any study procedures

## **5.2 Exclusion Criteria**

1. Patients with vasodilatory shock, orthostatic hypotension, hypotension, or tachycardia at screening/baseline
2. Patients experiencing cerebral hemorrhage or cerebral infarction at baseline
3. ALT/AST > 5 times the upper limit of normal; Child-Pugh Score 10 to 15.
4. Stage 4 severe chronic kidney disease or requiring dialysis (i.e. eGFR < 30)
5. Patients on mechanical ventilation or extracorporeal membrane oxygenation (ECMO)
6. Patients taking droxidopa
7. Pregnant and lactating women and those planning to get pregnant
8. Known or suspected allergy to the trial drug or the relevant drugs given in the trial
9. Presence of other disease that may interfere with testing procedures or in the judgement of the Investigator may interfere with trial participation or may put the patient at risk when participating in this trial
10. Know inability of patient to comply with the protocol for the duration of the study
11. Involvement in a clinical research study within 4 weeks prior to screening and/or prior enrollment in the study or plan to participate in another interventional clinical trial during the study period. Participation in observational registry studies is permitted.

## **5.3 Screening/Baseline/Randomization**

Screen failures are defined as patients who consent to participate in the clinical trial but are never subsequently enrolled. In this study, a patient can become a screen failure at any time during the screening visit (Visit 1), prior to randomization. In order to ensure transparent reporting of screen failure patients, meet the [Consolidated Standards of Reporting Trials \(CONSORT\)](#) publishing requirements, and respond to queries from Regulatory authorities, a minimal set of screen failure information is required including Demography, Screen Failure details, and Eligibility Criteria.

When a patient meets all eligibility requirements, study site personnel will consult the study database to obtain the patient's randomization number and treatment assignment.

Under no circumstances will patients randomized in the trial be permitted to be re-screened and randomized for a second time in this trial.

## **5.4 Premature Withdrawal and Discontinuation Criteria**

### **5.4.1 Withdrawal from Randomized Treatment or from the Study by Patient**

The patients have the right to withdraw from the trial at any time for any reason, without the need to justify their decision. However, the Investigator should record the reason for the patient's withdrawal, if

possible. Every effort should be made to encourage patients to remain in the study for the duration of their planned outcome assessment.

In case the patient has withdrawn consent, no new data can be entered into the e-CRF and data will be recorded in the medical records only. Correction of previous data entries and/or entering of data related to visits/procedures done prior to but made available after withdrawal of consent (e.g. laboratory results) will be allowed unless the patient disapproves it.

#### 5.4.2 Discontinuation of Study Drug

A patient in this clinical study may discontinue study drug for any of the following reasons:

- An adverse event which, in the opinion of the Investigator necessitates withdrawal of study drug
- A patient's substantial non-compliance (e.g. visits non-compliance)
- The Investigator's opinion that continuing the patient in the trial is not appropriate. The Investigator may withdraw a patient at any time if it is considered to be in the patient's best interest.
- Patient requests to discontinue study drug
- Patients who suffer vasodilative shock. However, physicians can use rescue therapy such as vasopressin to restore blood pressure and allow patients to continue in the study, at the discretion of the attending physician.
- Patients whose ALT/AST rise to >5x upper limit of normal or Child Pugh score of 10-15.
- Patients who experience a cerebral hemorrhage or cerebral infarction

Patients discontinued from study treatment should remain in the study and complete all remaining study assessments. If not possible, at a minimum, they should be invited to a Safety Follow-up Visit 7 days after the last dose of IP as soon as possible after a decision of discontinuation has been taken. At these visits, the Investigator will obtain all the required details and document the date of the premature termination and the main reason in the e-CRF. If the reason for study drug discontinuation is an adverse event, the specific event will be recorded in the e-CRF.

NOTE: patients that progress to mechanical ventilation during the study may remain on study drug and should not be withdrawn.

Definition of Dose Limiting Toxicity:

The occurrence of any of the following toxicities from the initial dose of Ifenprodil administration (in combination with Standard of Care (SOC)) which results in:

- a. The necessity to delay ifenprodil administration in the participant, OR
- b. To reduce the dose of ifenprodil administered, either for the participant, or for subsequent participants,

will be considered a DLT, if judged by the investigator to have a reasonable possibility of being related to the ifenprodil administration.

Severity is graded according to the NCI Common Terminology Criteria for Adverse Events (CTCAE), Version 5.0 equivalents of mild, moderate or severe:

1. Grade 3 or higher toxicity, except elevations in gamma-glutamyltransferase (GGT)

2. Grade  $\geq 3$  AST/ALT elevation
3. Grade  $\geq 2$  AST/ALT elevation with Grade  $\geq 2$  bilirubin elevation

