#### 5.4.3 Withdrawal of Patients from the Study

The Investigator also has the right to withdraw patients from the study post initial dosing. Whenever possible the patient should be followed for all assessments per protocol. Patients will be withdrawn in the following circumstances:

- Patients withdraws consent or requests discontinuation from the study for any reason
- Death of the patient
- Termination of the study
- Loss to follow-up (every effort must be made to contact the patient; phone calls on three separate days must be made, and a certified letter must be sent to the patient's most recent address)

Any withdrawal must be fully documented in the e-CRF and source documents, registered in the e-CRF as discontinued, and followed by the Investigator/Investigative Staff. Patients who withdraw from the study or are lost to follow-up after signing the informed consent form and randomization will not be replaced.

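### As written, the DLT definition does not flag toxicities that stop ifenprodil for good, and the SAP's by-term discontinuation table is titled for leaving the study, not for stopping the drug

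*Protocol*

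**What the plan says.** **DLT definition.** Protocol 5.4.2 lists three toxicity criteria and calls an event a DLT if the investigator sees a reasonable possibility of relation to ifenprodil and the event has one of two consequences: "The necessity to delay ifenprodil administration in the participant, OR" "To reduce the dose of ifenprodil administered, either for the participant, or for subsequent participants". SAP 12.1 repeats this definition and adds that DLTs will be marked in the adverse event listings.

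**Stopping the drug.** The same Protocol section names, among the reasons for ending study drug, "An adverse event which, in the opinion of the Investigator necessitates withdrawal of study drug". It also names vasodilative shock, liver enzyme rises above 5 times the upper limit of normal (or a Child-Pugh score of 10 to 15), and cerebral hemorrhage or infarction. Protocol 5.5 directs that ifenprodil be stopped at that same liver threshold. Protocol 8.2.2.5 records discontinuation, interruption and reduction as distinct actions.

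**After stopping.** Protocol 5.4.2 says: "Patients discontinued from study treatment should remain in the study and complete all remaining study assessments".

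**Outputs.** Protocol 10.10 says that treatment-emergent events leading to discontinuation from treatment will be tabulated, without fixing a format. SAP 12.2 has an overall summary that counts dose discontinuation of ifenprodil by arm. Its tables by System Organ Class and Preferred Term include one for events leading to study discontinuation.

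**The concern.** A DLT flag should mark the toxicities that prevented the planned dosing. Ending the drug permanently is the most consequential of the possible actions on dosing, and it is the one that the definition omits. Two people applying the rule could classify the same event differently, depending on whether they treat stopping as a form of delay.

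The table raises a related question. Phase 2b, the only stage this SAP covers, compares 20 mg and 40 mg TID with standard of care before Phase 3 is designed. The number of patients who discontinue the product because of an adverse event is a named safety endpoint (Protocol 3.2, SAP 2.4). A reader of the report will want to know which events stopped ifenprodil at each dose, and no table that the SAP lists is titled to show this.

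**Working it through.** The plan states no figure on this point and no calculation applies. The check compares the texts and counts the tables.

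**Step 1: the DLT rule against the action codes.** The rule names delay and reduction. Protocol 8.2.2.5 names discontinuation separately from interruption and reduction, so the protocol does not treat stopping as a kind of delay or reduction. Two invented patients, each with the same related, listed toxicity, show the effect:

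- Patient 1 has doses withheld and later resumes. Consequence (a) is met, so the event is a DLT.
- Patient 2 stops ifenprodil for good at onset, with no preceding delay and no reduction for later participants. Neither (a) nor (b) is met on the words, so the event is not flagged.

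Patient 2 is not a contrived case, because 5.4.2 and 5.5 plan for stopping. The documents do not map the 5-times liver threshold to a toxicity grade, so nothing here depends on that mapping.

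**Step 2: the by-term tables in SAP 12.2.** They cover: all events; serious events; grade 1 or 2; grade 3 or more; ifenprodil-related; related to standard of care; ifenprodil-related serious; serious related to standard of care; leading to study discontinuation; leading to death. That is 10 tables. Those titled for discontinuation of ifenprodil: 0. Those titled for study discontinuation: 1.

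**Step 3: are the two discontinuations the same event?** Not under 5.4.2, which asks patients who stop the drug to stay and be assessed. If Patient 2 is handled as intended, the event does not enter the study-discontinuation table. SAP 13, on changes to the planned analysis, mentions only an ad-hoc remdesivir analysis and does not explain a move from treatment to study discontinuation.

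**Step 4: where Patient 2 does appear.**

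- In the overall summary, under dose discontinuation of ifenprodil, by arm.
- In the adverse event listing, with Preferred Term, System Organ Class, action taken and causality.
- In the exposure listing (SAP 10), with the reason drug was not given.
- In whichever severity and relatedness tables apply. Events at grade 2, which can satisfy the third DLT criterion, fall in the grade 1 or 2 table. None of these tables separates events that stopped the drug from those that did not.

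What is missing is therefore the DLT flag on Patient 2's event and a by-term table of drug-stopping events.

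**The case against.** The strongest reply is that nothing depends on the gap. The protocol states that "there are no pre-specified study stopping rules for safety", and DLTs are only marked in listings. They drive no dose choice, endpoint or monitoring trigger. That stands, and it limits the importance of the point.

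Second, the reporting promise may already be kept. Protocol 10.10 does not ask for a by-term format, and the overall count by arm reports the named endpoint. With about 50 patients per arm, the drug-stopping terms can be read from the listing. This also stands: no breach of a stated requirement is shown, and a reader who infers one goes too far.

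Third, the table title may be loose wording. Protocol 5.4.2 mixes stopping the drug with leaving the trial, and 7.3.4 describes patients invited 7 days after their last dose as having discontinued from the study. SAP 16 leaves table content to mock shells that are not available. This is a fair doubt and lowers confidence in the second half to moderate.

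Fourth, stopping a fixed TID schedule of at most 14 days also means that doses are withheld, so an investigator could count it under (a). That is a sensible reading, but neither document states it, and 8.2.2.5 keeps the actions apart.

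A reader might also infer that the study-discontinuation table would be nearly empty, because the list in 5.4.3 that begins "Patients will be withdrawn in the following circumstances" names no non-fatal adverse event. The documents do not support that. The list includes a patient's request for any reason, 8.6.2 leaves withdrawal after a serious event to the investigator, and 8.3 foresees laboratory abnormalities that end participation.

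**Conclusion.** The point holds as a minor safety-reporting gap. The first half, that the literal DLT definition leaves out toxicities ending ifenprodil outright, rests directly on matching text in both documents. The second half, that the by-term table as titled targets a different event from the one in Protocol 10.10, holds with moderate confidence. It assumes that the title means what it says.

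A reader might infer that drug discontinuations for adverse events go unreported, or that patient protection is weakened. Neither follows. The discontinuations are counted by arm and listed by patient, and the safety reviews by the DSMB and the medical monitor do not use the DLT definition. Sample size, error rates and efficacy analyses are untouched. The documents give no rate from which to estimate how many events would be misclassified.

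**What to change.** 1. In Protocol 5.4.2 and SAP 12.1, add a third consequence to the DLT definition: *or to permanently discontinue ifenprodil*.
2. In SAP 12.2, add a table of treatment-emergent events leading to discontinuation of ifenprodil, by System Organ Class and Preferred Term, for Arms A and B. If the study-discontinuation table was meant to show this, retitle it instead.

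The cost is one clause in two documents and one added or retitled table. No new data should be needed, because Protocol 5.4.2 already provides: "If the reason for study drug discontinuation is an adverse event, the specific event will be recorded in the e-CRF". The downside is one extra table and possibly more events flagged as DLTs.

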#### 5.4.3 Withdrawal of Patients from the Study

The Investigator also has the right to withdraw patients from the study post initial dosing. Whenever possible the patient should be followed for all assessments per protocol. Patients will be withdrawn in the following circumstances:

- Patients withdraws consent or requests discontinuation from the study for any reason
- Death of the patient
- Termination of the study
- Loss to follow-up (every effort must be made to contact the patient; phone calls on three separate days must be made, and a certified letter must be sent to the patient's most recent address)

Any withdrawal must be fully documented in the e-CRF and source documents, registered in the e-CRF as discontinued, and followed by the Investigator/Investigative Staff. Patients who withdraw from the study or are lost to follow-up after signing the informed consent form and randomization will not be replaced.

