### **8.5 Pregnancy**

All pregnancies or suspected pregnancies occurring in either a female patient or partner of a male patient must be reported immediately. The IP should be discontinued, and the patient withdrawn from the trial.

The Investigator will follow the female patient until completion of the pregnancy and collect the outcome of the pregnancy (either normal or abnormal outcome).

If the outcome of the pregnancy was abnormal, the Investigator should report the abnormal outcome as an AE. If the abnormal outcome meets any of the serious criteria, it must be reported as an SAE within 24 hours of the Investigator's knowledge of the event. All neonatal deaths that occur within 28 days of birth should be reported, without regard to causality, as SAEs. In addition, any infant death after 28 days that the Investigator suspects is related to the in-utero exposure to the IP should also be reported within 24 hours of the Investigator's knowledge of the event.

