### **8.6.2 Reporting of Treatment Emergent SAEs**

In order to meet the requirements for expedited reporting of SAEs meeting specific requirements to applicable regulatory authorities and IRB/IEC, all SAEs, must be reported to the Sponsor within 24 hours from the time the site investigational team first become aware of the event using the appropriate method as outlined in the Safety Reporting Guidelines.

As further information regarding the SAE becomes available, such follow-up information should be documented on a new SAE report form, marked as a follow-up report, and reported using the appropriate method as outlined in the Safety Reporting Guidelines.

Withdrawal from the study in the event of an SAE and therapeutic measures taken shall be at the discretion of the Investigator. A full explanation for the discontinuation from the study should be made in the patient's medical records and in the eCRF.

A planned hospitalization will not be a requirement of SAE reporting.

The Investigator is required to ensure that the data on these forms is accurate and consistent.

This requirement applies to all SAEs (regardless of relationship to IP) that occur during the study (from the time the patient signs informed consent until 7 days after the last dose of IP) or any SAE made known to the Investigator at any time thereafter that is suspected of being related to IP.

The SAE report should provide a detailed description of the SAE and include a concise summary of hospital records and other relevant documents. If a patient died and an autopsy has been performed, copies of the autopsy report and death certificate are to be sent to the Investigator as soon as these become available.

Where required by local legislation, the Investigator is responsible for informing the IRB/IEC of the SAE and providing them with all relevant initial and follow-up information about the event. The Investigator must keep copies of all SAE information on file, including correspondence with the IRB/IEC.

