3.3 Handling of Missing Data

All data will be analysed as collected and missing values will not be imputed or replaced unless stated otherwise.

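### Patients who stop study drug are to stay in follow-up, but Protocol 5.4.2, 5.4.3 and 8.6.2 let the open-label investigator withdraw them from the study, so poor Day 15 outcomes can go missing unequally by arm

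*Protocol*

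**What the plan says.** Protocol 5.4.2 separates stopping drug from leaving the study: "Patients discontinued from study treatment should remain in the study and complete all remaining study assessments". If that is not possible, "at a minimum, they should be invited to a Safety Follow-up Visit 7 days after the last dose of IP". The same section also says: "The Investigator may withdraw a patient at any time if it is considered to be in the patient's best interest".

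Protocol 5.4.3 adds: "The Investigator also has the right to withdraw patients from the study post initial dosing". It gives no criteria for using this right, but continues: "Whenever possible the patient should be followed for all assessments per protocol".

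Protocol 8.6.2: "Withdrawal from the study in the event of an SAE and therapeutic measures taken shall be at the discretion of the Investigator". This sentence carries no follow-up clause.

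Protocol 8.5, on pregnancy in a patient or a male patient's partner: "The IP should be discontinued, and the patient withdrawn from the trial".

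Protocol 7.3.4 invites patients who have discontinued from the study to a safety visit 7 days after their last dose, on the Visit 3 schedule. It does not mention Day 15 for them. The synopsis puts withdrawal and discontinuation criteria under one heading.

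On analysis, SAP 3.3 says "missing values will not be imputed or replaced unless stated otherwise". The only exception for the primary endpoint is in SAP 11.1, where a WHO-7 score of 7 is carried forward after death. The model code there has no step for a missing response. Protocol 4.4 states that investigators know the arm in Phase 2b, and 5.4.3 states that withdrawn patients are not replaced.

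**The concern.** A site with a drug-arm patient who has an SAE cannot tell whether 5.4.2 (keep the patient in the study) or 8.6.2 (withdrawal at discretion) governs. If the patient is withdrawn, nothing in the protocol requires a Day 15 WHO-7 score. The patient remains in the ITT population by definition but contributes nothing to the proportional odds model.

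Patients withdrawn after an SAE are more likely than others to be in a poor category on Day 15. The decision is taken knowing the arm. The right in 5.4.3 is tied to dosing, which SOC-only patients never have, and the drug-stopping triggers in 5.4.2 are ones that SOC patients do not face. The loss is therefore likely to be unequal between arms, and a larger loss of poor outcomes from the drug arms would move the common odds ratio towards ifenprodil.

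Phase 2b informs the Phase 3 endpoint and sample size (Protocol 4.1, 4.2, 10.3), and SAP 11.1 allows p < 0.05 to be read as potentially promising. A modest distortion could carry into those decisions.

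**Working it through.** **1. Can the rules leave Day 15 blank?** A patient whose last dose is on Day 4 and who is discontinued from the study is invited for Day 4 + 7 = Day 11. Any last dose before Day 8 puts that visit before Day 15. SAP 3.3 imputes nothing and SAP 11.1 fills in only deaths. So yes, for a surviving patient, and for a patient whose later death is not captured.

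**2. Inputs.** Table 2, SOC, categories 1 to 7: 37, 36, 17, 5, 2, 1, 2%. There are 50 evaluable patients per arm (Protocol 4.1), and the test is two-sided at 0.025 per dose (SAP 11.1). The point rests on no figure stated in the plan. As a check on the input, Table 2's treatment column follows from its SOC column: category 1 has odds (0.37/0.63) × 1.75 = 1.028, or 50.7%, as printed.

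**3. Assumed, because the documents give no rate:** no drug effect; a fraction f of drug-arm patients in categories 4-6 has no Day 15 score; deaths are kept; SOC is complete. Categories 4-6 hold 5 + 2 + 1 = 8%, or 4 of 50.

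**4. Effect on the odds ratio.** With f = 0.5 the drug arm keeps 96% of its patients. Cumulative percentages become 37/0.96 = 38.5 (category 1), 73/0.96 = 76.0 (1-2) and 90/0.96 = 93.75 (1-3), against 37, 73 and 90 in SOC. The cumulative odds ratios at these cuts are 1.07, 1.17 and 1.67. At the cut below death the ratio is 0.96, because deaths are kept in a smaller denominator. A proportional odds fit to the expected proportions gives the common odds ratio for better status:

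| Drug-arm category 4-6 patients lost | Share of that group | Apparent OR |
|---|---|---|
| 1 of 50 | 25% | 1.06 |
| 2 of 50 | 50% | 1.13 |
| 3 of 50 | 75% | 1.21 |
| 4 of 50 | 100% | 1.30 |

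**5. Effect on the test.** These are 20,000 simulated trials per case, using the tie-corrected Wilcoxon test (the unadjusted proportional odds score test). The rejection rate at 0.025 is 0.025 with no loss, 0.031 with half lost and 0.060 with all lost. At the 0.05 level the rates are 0.049, 0.061 and 0.106.

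**6. A harmful drug.** Applying OR 0.75 to the SOC column puts 10.3% of the drug arm in categories 4-6, about 5.1 of 50. Losing half of them (about 2.6) with deaths kept moves the apparent OR from 0.75 to 0.86.

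**7. Sensitivity.** With an assumed sicker distribution (20, 25, 15, 15, 8, 7, 10%), losing half of categories 4-6 (15% of the arm) gives OR 1.32 and a rejection rate of 0.067 at the 0.025 level, 50 per arm.

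**The case against.** The protocol has safeguards. Section 5.4.3 asks for follow-up whenever possible and says that withdrawals are to be followed by site staff. Section 5.4.1 asks for every effort to keep patients for their planned outcome assessment, and bars new e-CRF data only when the patient withdraws consent. SAEs are followed until resolved or stable (8.2.2.6, 8.7). Ventilated patients should not be withdrawn (5.4.2), and known deaths are carried forward. Patients in categories 4-6 are inpatients, so their status is normally in the chart. SAP 11.1 calls this phase essentially exploratory, and Phase 3 is planned with placebo and double-blinding.

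Most of this stands, and it makes the loss avoidable. It does not remove the conflict. A request in 5.4.3 does not clearly override a discretion in 8.6.2 that lacks it, following an SAE is not the same as recording a Day 15 WHO-7 score, and 7.3.4 points sites to a different visit.

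Four stronger readings are tempting, but the documents do not support them:

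- **The loss is wholly one-sided.** Sections 8.5 and 8.6.2 are worded for all arms, 8.6.2 covers SAEs regardless of relationship to drug, and the 5.4.2 sentence on withdrawal at any time has no dosing condition. Likely unequal is as far as the text goes.
- **Survival results are biased towards the drug.** Recorded deaths stay in the primary analysis, and no effect on mortality has been calculated. Only deaths missed after withdrawal are exposed.
- **Pregnancy withdrawals hide bad outcomes.** Pregnancy is not a poor COVID-19 outcome, pregnant women are excluded, and dosing lasts at most 14 days. Section 8.5 is a wording inconsistency that adds little bias.
- **The absence of SAEs from the 5.4.3 list is itself a contradiction.** That list gives circumstances in which patients will be withdrawn; withdrawal after an SAE is discretionary.

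**Conclusion.** The passages conflict, and following them as written can remove non-fatal poor outcomes from the primary model. The size cannot be derived from the documents, because the removal fractions are assumed. Under Table 2 with 50 per arm the distortion is modest: OR 1.13 and a rejection rate of about 0.031 if half of the drug-arm category 4-6 patients are lost. It reaches 1.30 and about 0.060 only if every one of them is lost. These figures slightly overstate the exposure, since they remove category 6 (1%, or half a patient in 50) along with categories 4 and 5, although ventilated patients should not be withdrawn. A larger effect needs a sicker population than Table 2 assumes. The case for acting is that the remedy is cheap and protects the primary endpoint of an open-label trial; the documents do not show that a serious bias will occur.

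**What to change.** Reconcile Protocol 5.4.2, 5.4.3, 7.3.4, 8.5, 8.6.2 and the merged synopsis heading so that an investigator's decision, whether after an SAE, for pregnancy or for any other reason, concerns study drug only and does not end follow-up. This must include the 5.4.2 sentence on withdrawal at any time; otherwise a cross-reference to 5.4.2 would bring the same discretion back.

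Limit the end of follow-up to withdrawal of consent to follow-up, loss to follow-up, study termination, or death (scored WHO-7 = 7). In 7.3.4, make the 7-day safety visit additional to the Day 15 and Day 29 assessments. Collect Day 15 and Day 29 WHO-7 status and Day 60 vital status for every randomised patient, from the chart or remotely if needed; 7.3.3 already allows remote methods for Days 15 and 29, and 7.3.5 a telephone call for Day 60.

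No drug-stopping rule changes, and no view is taken here on when drug should be stopped. The sample size does not change. The cost is protocol wording and site retraining, with no new scheduled visits or procedures.
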